If treated with a TLSO brace, many idiopathic scoliosis patients would conceivably be subjected to years of brace wear and the cost and psychological factors inherent therein. Additional downsides of brace treatment include the potentially negative psychosocial impact of wearing an external sign of deformity during adolescence, a key period of emotional development. Prior research has identified negative psychosocial effects related to wearing a brace in children.

Recent evidence has suggested that certain curve patterns will likely progress to 50 degrees or more, despite treatment with a TLSO brace. Sanders, et al. demonstrated a correlation of Cobb angle (greater than 35 degrees) and skeletal maturity (bone age 4 or less) to the risk of progression to 50 degrees or more, despite TLSO bracing. The evidence supports that the current practice of TLSO bracing is not an effective treatment to avoid progression to 50 degrees in these patients. It is on this population (thoracic Cobb angle greater than 35 degrees, bone age of 4 or less) that we intend to test the safety and efficacy of anterior vertebral body tethering to avoid curve progression to 50 degrees.

Objectives:

The objectives of this study are to assess the safety and feasibility of anterior vertebral body tethering surgery to treat idiopathic scoliosis.

Study Design:

This is a pilot study, non-randomized, open label study of the anterior insertion of an Anterior Vertebral Tether Device in pediatric scoliosis. The study will be conducted at a single site - The Children's Hospital of Philadelphia.

Setting/Participants:

This is a single-site, Sponsor-Investigator led pilot study of vertebral body tethering for pediatric idiopathic scoliosis in children aged 8-16 years.

Study Interventions and Measures:

The study intervention is surgical orthopedic implantation of the Anterior Vertebral Tether Device, by way of thoracoscopic surgery under general anesthesia. The primary outcome measures include assessments of safety of the insertion procedure and of the device, as well as the secondary measure of feasibility by determining the ability to successfully implant the investigational device. Monitoring will be conducted by a Safety Officer, who has extensive training and experience in surgical procedures.

PROTOCOL SYNOPSIS

Study Title	Safety and Feasibility of a Vertebral Body Tethering Technique for Pediatric Idiopathic Scoliosis
Funder	Departmental Funds
Clinical Phase	Pilot Study

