The prospective studies of bracing have led to analysis of various subpopulations treated with bracing and published literature suggests that bracing is ineffectual for those patients who are early in the skeletal maturation process. The most important difference in the results presented by Weinstein and colleagues [13] and Katz and colleagues [12] and the proposed study is the level of maturity (and therefore natural history) of the treatment population. The average age of initiation of bracing in both the Weinstein et al. and Katz et al. studies was 12.7 years. In a subsequent study of AIS patients treated with bracing from the Katz et al. study, Karol and colleagues demonstrated a more than five-fold increased risk of bracing failure in Risser 0 patients compared to Risser 1 patients [14]. The study results of Karol et al. and others suggest that there may be a level of skeletal immaturity below which bracing

cannot alter the natural history of moderate idiopathic scoliosis [15]. The study reported that 63% of patients with Risser 0 and open triradiate cartilage progressed to the point of requiring a fusion. The efficacy of bracing in this cohort was significantly less than those with closed triradiate cartilages ($P<0.001$). Furthermore, those patients with Risser 0, open triradiate cartilage, and a Cobb angle of 30 degrees or greater had a 74% incidence of progression to fusion. Jarvis and colleagues [16] reported that fusion was avoided in only 49% of those patients with juvenile idiopathic scoliosis (JIS) treated with bracing, which raises the question of whether bracing has any impact on the natural history in JIS. Charles et al. further stratified JIS by Cobb angle [17]. The study showed that curves more than 30 degrees prior to the puberty growth spurt progressed to a magnitude requiring surgery in 100% of cases despite bracing.

For these reasons, the practice of the Sponsor-Investigator is to perform a spinal fusion in those patients with a curve less than 50 degrees who would have a high likelihood of progression to a Cobb angle beyond 50 degrees and in whom bracing would likely fail. The decision making by the PI exactly mirrors the inclusion criteria: a) those patients who meet the parameters for inclusion would otherwise be offered a spinal fusion, and b) those who do not meet the inclusion criteria would be recommended bracing or observation.

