6.3.2 Safety Analysis

The safety endpoint will be factors associated with the adverse events in patients that have undergone anterior VBT surgery. Variable reporting for adverse event will be dichotomous. Descriptive statistics will be used to report number and type of adverse events. Further, chi-square or Fisher's-exact test analysis will be used to identify variables that correlate with adverse events following anterior tethering surgery. Further, logistic regression will be conducted to clarify which variables are associated with adverse outcomes. Odds ratio along with confidence intervals will be reported.

All subjects will begin the safety analysis at Study Day 0 (day of surgery). Intraoperative and post-intervention medical events or signs and symptoms of the complications arising after the start of study intervention will be captured using list of common events associated with anterior VBT surgery. Adverse signs, symptoms, and/or laboratory abnormalities already existing prior to the baseline visit will be captured in the medical history assessment. The date of onset, severity, and end date (if relevant) will be documented.

Medical events resulting from any procedure performed in the study will be collected as adverse events (AEs). The event description, date of onset, end date, severity, and outcome will be documented for the study-related AEs. The frequencies of AEs by type, body system, severity and relationship to study intervention will be summarized. SAEs (if any) will be described in detail. A distinction will be made between those AEs/SAEs which are “device-related”, those which are “not device-related”, and those which are “uncertain to be related”. “Device-related” complications will include any events directly related to the integrity, safety, or biomechanics of the Anterior Vertebral Tether Device composed of the investigational staples, screws, locking caps, and PET cord. Device-related AE incidence will be summarized along with the corresponding exact binomial 95% two-sided confidence intervals.

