6.6.1 Stopping rules for any SAE related to the study procedure (surgery)

- SAE in all of the first 5 patients or
- SAE in 7 of first 10 patients or
- SAE in greater than 50% of patients after 15 cases

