8.4.1 Relationship of AE/SAE to study intervention or device

The relationship of each Event to the study intervention should be characterized using one of the following terms in accordance with CHOP IRB Guidelines: **definitely, probably, possibly, unlikely, or unrelated**. In this case, the “study intervention” is considered to be the surgical intervention and implantation of the medical device (*Anterior vertebral body tethering surgery under general anesthesia with spinal cord monitoring*). This includes (but is not limited to) induction of anesthesia, incision and surgical approach, device implantation, and recovery. **For each SAE, the PI and Safety Officer will make a case-by-case determination on the relationship of the SAE to the study procedure, which will be documented in the study documents.**

There will be further classification of the Event as either “device-related”, “not device-related”, or “uncertain to be device-related”. Device-related adverse events are those events directly related to the integrity, safety, or biomechanics of the implanted device. This can include variables like device breakage or device migration. Other adverse events which are considered not device-related are those that are related to the act of the surgery and medical recovery (anesthesia, incision and surgical approach, post-operative recovery, etc.). This distinction will be indicated in the study documents. **For each Event, the PI and Safety Officer will make a case-by-case determination on whether the Event is “device related”, “not device related”, or “uncertain”. An event which is classified as “device related” will be considered an Adverse Device Effect. Adverse device effects have special reporting guidelines, as outlined below.**

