A Limited Data Set, including images, will be transferred from CHOP to Globus Medical, Inc. as part of a license agreement executed between the two parties for use in the manufacturer's humanitarian device exemption (HDE) submission. Images will be limited to images of subjects' torsos and will not include video recordings, subject faces, or identifiable features. Data will be sent by secure electronic file transfer and with hardcopy source documents. Hardcopy documents will be redacted to remove identifiers and be transferred via courier or in-person from study team member to an authorized representative of Globus Medical, Inc. Data transferred will

not include PHI, except dates of service, and Globus Medical, Inc. will not have access to the master list to link data back to subjects.

3. Security:

The master sheet will be a password protected Excel file kept in the secure orthopedic research drive at CHOP. The REDCap MySQL database is replicated in real time to a completely redundant instance of MySQL. The redundant instance is available for restoration of the primary database or for manual failover in the case of primary database failure. Time-stamped backup files are made from the replicated database daily by CHOP Research Information Systems using automated backup routines. Backup files are encrypted and transferred to a secure file server accessible only to designated personnel. A rolling seven-day window of backup files is maintained in an immediately available online state, with a larger window maintained in a compressed file archive available at a reduced speed of access. Daily destructive database backup files are stored on the database server and are deleted only after successful backup of the entire database to file. In the event of data error, loss or corruption, research personnel will work with CHOP Research Information Systems to determine the most appropriate recovery strategy. Data and backups are stored in the CHOP Research Information Systems Storage Area Network (SAN). Access to the SAN directories where data are stored will be limited to Research Information Systems personnel, with authentication performed using CHOP's enterprise Active Directory service. The data from the application will be compiled on a secured survey web platform that is encrypted using AES 256 bit encryption. The data collected on paper forms during testing will be secured in the patient-specific study binders in a locked research office.

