9.3.2.3 Risks associated with live case demonstration:

- Extended anesthesia exposure: Time under anesthesia may be extended minimally, at most a few minutes, due for example to additional setup procedures, however, this preparation will be done by specialized staff in tandem with the standard surgical preparation to not add extra time under anesthesia.
- Infection risk: There may be added risk of infection with more personnel and additional equipment in the room. However, any additional staff that may be in the operating room will be educated on safe clinical practices when entering and will remain outside of the sterile field during observation. Only the surgeon and other relevant clinicians will be allowed in the sterile field. Any additional equipment used will be covered with sterile cloth and utilized only as necessary during the procedure.
- Surgeon distraction: This risk will be addressed by having a separate surgeon handling commentary of the procedure, allowing the performing investigator and surgical team to continue the surgery as would normally be conducted without distraction.

- Breach of confidentiality: There is a risk of loss of privacy if identifying information is inadvertently disclosed during the surgery. Staff will be aware to not disclose identifying information during the surgical case, unless necessary. If identifying information is disclosed, the videotaped record will be edited to remove those frames. No recording system can completely guard against risks such as a breach caused by an intentional intrusion, inadvertent disclosure of information, or the failures or limitations of equipment used to transmit live or recorded data.

The investigators believe these additional risks associated with the live case demonstration are minimal.

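### Relatedness of adverse events rests on one joint, unmasked call by the PI and the Safety Officer, with neither view kept and no rule for disagreement; it feeds the 6.6.1 stopping count and the device-related rate

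*Combined protocol and SAP*

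**What the plan says.** **Who decides.** Section 8.4.1 provides that for each SAE "the PI and Safety Officer will make a case-by-case determination on the relationship of the SAE to the study procedure". Device-relatedness is handled the same way: "For each Event, the PI and Safety Officer will make a case-by-case determination on whether the Event is" device related, not device related or uncertain. The outcome has to be documented, but the section does not ask for each assessor's view.

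**Who they are.** The Abstract states: "This is a single-site, Sponsor-Investigator led pilot study of vertebral body tethering". Section 3.2 says the study is not blinded. The Safety Officer is described by surgical training and experience. Section 9.3.1 says safety monitoring is handled internally with the hospital's compliance office, and that the PI and study team take part in the interim safety analyses.

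**What uses the call.**
- The heading of 6.6.1 limits that stopping rule to SAEs related to the surgery: "Stopping rules for any SAE related to the study procedure (surgery"). Its limits are 5 of the first 5 patients, 7 of the first 10, or more than 50% after 15 cases.
- Section 6.3.2 plans one interval for an event rate: "Device-related AE incidence will be summarized along with the corresponding exact binomial 95% two-sided confidence intervals".
- Section 8.5 records all AEs to POD 90 and all SAEs to POD 730, but after POD 90 it records non-serious AEs only if they are judged device related.

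**What is left open.** Section 8.4.1 grades relation to the intervention in five levels, while 6.6.1 does not say which of them count as related. Nor does the plan say how *uncertain* device events enter the 6.3.2 incidence.

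**The concern.** Attribution in an open, single-arm surgical study is a judgement, and here one of the two people making it leads and sponsors the study. When two assessors settle on one answer in discussion, the record cannot show how often they began apart or which way the differences were resolved. A tendency to call borderline events unrelated would lower the device-related rate, make a 6.6.1 halt less likely and keep some late non-serious events out of the study record. The first two could be partly re-examined later from recorded events. The third could not, because an unrecorded event leaves nothing in the study documents to reclassify.

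The 6.6.1 limits are already high, so they have little slack for under-attribution when the true rate lies near them.

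**Working it through.** The plan states no operating characteristics for its stopping rules, so there is no figure of its own to reproduce. The check has two parts.

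**1. Which outputs pass through the relatedness call**

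| Output | Section | Filtered by the call? |
|---|---|---|
| Overall AE rate to POD 90 | 6.1, 8.5 | No: all AEs recorded |
| SAE rate to POD 730 | 6.1, 8.5 | No: recorded regardless of cause |
| Procedure-related stopping count | 6.6.1 | Yes |
| Device failure stopping counts | 6.6.2 | Little: defined failures needing re-operation |
| Device-related incidence and exact CI | 6.3.2 | Yes |
| Non-serious AEs after POD 90 | 8.5 | Yes: recorded only if device related |

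**2. How far under-attribution could move the filtered outputs (illustration)**

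Inputs from the plan: the three limits in 6.6.1 and up to 40 subjects (6.4). Assumed, because the plan gives no values: a true share *p* of patients with a procedure-related SAE, and a share *m* of those patients classed as unrelated. The counted rate is then q = p(1 − m). Patients are treated as independent, with a look after every patient and all misclassification in one direction.

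Let f(n, k) be the probability of k counted patients among n with no halt so far. Then f(n, k) = f(n−1, k)(1 − q) + f(n−1, k−1)q. Mass is removed as a halt when k = 5 by n = 5, when k ≥ 7 by n = 10, or when 2k > n for n from 15 to 40. The chance of ever halting is the total mass removed.

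Single-look components for p = 50%, with m = 0 (q = 0.50) and m = 20% (q = 0.40):
- 5 of 5: 0.50⁵ = 0.031; 0.40⁵ = 0.010.
- P(X ≥ 7 of 10): 0.172; 0.055.
- P(X ≥ 8 of 15): 0.500; 0.213.

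Whole rule to 40 patients, chance of ever halting:

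| True rate p | m = 0 | m = 10% | m = 20% |
|---|---|---|---|
| 40% | 33.0% | 19.9% | 10.5% |
| 50% | 72.8% | 53.1% | 33.0% |
| 60% | 95.8% | 85.2% | 65.3% |
| 70% | 99.9% | 98.2% | 89.8% |

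The rule depends only on q, so p = 50% with m = 20% (q = 0.40) gives the same 33.0% as p = 40% with no misclassification.

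Device-related incidence, exact (Clopper-Pearson) 95% intervals at n = 40, counting patients with at least one event: 8/40 = 20.0% (9.1% to 35.6%). If 2 of the 8 are classed as not device related or uncertain, the result is 6/40 = 15.0% (5.7% to 29.8%).

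**The case against.** Several things limit the point, and four stronger readings are tempting but unsupported.

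- **A reader might infer that the primary endpoint is filtered.** It is not. Section 6.1 defines it as the rate of AEs/SAEs, 8.3 requires no causal link, and 8.5 records all AEs to POD 90 and all SAEs to POD 730. Only late non-serious AEs are lost, and the primary objective in 2.1 concerns the immediate post-operative period.
- **A reader might infer that the device stopping rules in 6.6.2 are equally exposed.** They count loosened components, tether failure and implant re-operation. Such events concern device integrity, which 8.4.1 itself classes as device related, so the label has little room to act. The need for re-operation is a clinical decision, but a different one.
- **A reader might look only at the ten-patient limit.** At a true 70% rate with 20% misclassified, the chance of 7 or more in the first 10 falls from 65% to 29%. That ignores the limit applying from 15 cases. Over the whole rule the fall is from 99.9% to 89.8%, so the main effect there is a later halt.
- **A reader might infer a personal financial interest.** Section 9.1 says data go to the manufacturer "as part of a license agreement executed between the two parties", the parties being the hospital and the manufacturer. It gives no terms and no interest of the PI, and funding is departmental. The text also does not say that the PI operates on every subject. Section 1.1.2 describes his surgical practice ("the practice of the Sponsor-Investigator is to perform a spinal fusion in those patients with a curve less than 50 degrees") and the live-case text in 9.3.2 refers to the operator as an investigator ("allowing the performing investigator and surgical team to continue the surgery as would normally be conducted without distraction"), which makes it likely but not stated.

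The defence also has substance. A second assessor with surgical experience is named. The intervention is defined to include recovery, so scope for calling an SAE unrelated to the procedure is narrow, and an event moved out of the device-related class as surgical still counts in 6.6.1. The plan summarises AEs by relationship, describes SAEs in detail, keeps source notes in the binder and sends Safety Officer reports to the IRB. For a descriptive study of up to 40 subjects, two-person attribution is a legitimate choice. What these safeguards do not supply is each assessor's own call, a rule for disagreement, or any trace in the study documents of late non-serious events judged not device related.

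**Conclusion.** The point stands in limited form. The joint determination in 8.4.1 is more open to bias than it needs to be. It governs the 6.6.1 count, the device-related incidence with its exact interval, and the recording of non-serious AEs after POD 90. The documents do not show that bias occurs, and its size cannot be derived from them.

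The loss for 6.6.1 depends on how close the true rate is to the limits. At a true 50%, the chance of ever halting goes from 73% to 53% or 33% with 10% or 20% of related SAEs classed unrelated. At 70% the rule remains robust, at 98.2% or 89.8%. These figures rest on assumed true rates, assumed one-way misclassification, independent patients and a look after every patient. The unstated meaning of related in 6.6.1 and the unstated handling of *uncertain* events are missing details that belong in the same edit. They are not the main issue.

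**What to change.** In 8.4.1:

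1. The existing Safety Officer classifies each event first, on both scales, without seeing the PI's call. The PI then classifies it, and both calls stay on the CRF.
2. Where they differ, the more-related category is used for the 6.6.1 count, the 6.3.2 device-related incidence and the decision to record a non-serious AE after POD 90.
3. The number of disagreements is reported with the safety results.

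In the same edit, state which of the five levels count as related in 6.6.1, and report the device-related incidence with and without *uncertain* events. For that comparison to cover the later period, 8.5 should say that non-serious events classed *uncertain* after POD 90 are recorded too.

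The cost is a few sentences and one extra CRF field, with no new staff and no change to the stopping limits. The downside is that the reported related rates may be slightly less favourable, since disagreements are resolved toward relatedness. Reporting the number of disagreements lets a reader judge how much of the rate that explains.

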8.5 Recording plan for AEs/SAEs

Surgery and Post-operative Phase (Day 0 – POD 90):

For these phases, all AEs (including SAEs) will be noted in the study records and reported per IRB and FDA requirements outlined below. The subjects will be encouraged to contact the office with any concerns, and the medical record will be monitored by study staff for indications of AEs.

Extended Follow-up Phase (POD 91-POD 730):

For this phase, all SAEs will be recorded (regardless of cause). Only AEs which are deemed “device related” will be recorded on study documents and reported per IRB and FDA requirements outlined below. The subjects will still be encouraged to contact the office with any concerns, and the medical record will be monitored by study staff for indications of SAEs or device-related AEs.

Long-term Follow-Up (POD 730 through approximately two years after skeletal maturity):

An observational study involving chart review of medical charts from CHOP and external sources as needed will be undertaken for long-term follow-up. All SAEs identified from the medical records that are considered device related, up to two years after skeletal maturity, will be reported in accordance with FDA requirements. This will be performed under a separate research protocol.

Only the AEs/SAEs indicated above will be recorded in a patient-specific study binder, kept in the secure orthopedics research office. The binder will contain a full description of the event, including the nature, date and time of onset, determination of non-serious versus serious, intensity (mild, moderate, severe), duration, causality, and outcome of the event. Hard copies of the primary documents (medical record notes) describing the event and any associated treatment will be printed and kept in the patient-specific study binder. A redundant copy of adverse events will be kept in the study REDCap database and will be maintained by the study team separately from the patient-specific study binder. The study binder will serve as the official record of all Events.

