3.3 Study Duration, Enrollment and Number of Sites

3.3.1 Duration of Study Participation

The subject will be followed for at least eight visits over a two year (730 day) period: one day for recruitment/consent, one day for the study intervention (surgery), one day for each visit: POD21, POD45, POD90, POD180, POD365, and POD730. These visits follow the schedule for a patient's standard-of-care follow-up for anterior spinal surgery. Any off-study visits within the study window will not be captured, unless they are related to an AE/SAE. There is a three-week grace period for post-operative study visits, and a 90 day grace period for extended follow-up visits, making the initial study participation period 730 + 90 days after the day of surgery. Long-term follow-up through at least two years following skeletal maturity will take place through a separate observational study.

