4.4.3 Visit 8 (POD 730)

- X-ray: AP/PA and lateral spine
- X-ray: Bending bolster films (completed at treating physician's discretion)
- Pulmonary function test (completed at treating physician's discretion)
- History and physical exam with height and weight
- Research specific physical exam (research)
- Medical record review and abstraction (research)
- X-ray review and abstraction (research)
- Complications review (research)
- Clinical photographs (research)
- SRS 30 Questionnaire (research)
- Study completion CRF (research)

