4.7 Subject Completion/Withdrawal

Subjects may withdraw from the study at any time without prejudice to their care. They may also be discontinued from the study at the discretion of the Investigator for lack of adherence to study treatment or visit schedules, AEs, or due to non-compliance. However, in order to collect important study-related data for this investigational device, as much as is feasible, the Investigator and study team will make efforts to follow-up subjects who do not strictly adhere to timely visit schedules. The Investigator and study team may do this via emails, phone calls, or letters. The Investigator may also withdraw subjects who violate the study

plan, or to protect the subject for reasons of safety or for administrative reasons. It will be documented whether or not each subject completes the clinical study. If the Investigator becomes aware of any serious, related adverse events after the subject completes or withdraws from the study, they will be recorded in the source documents and on the CRF.

Subjects who are withdrawn from the study during the post-operative follow-up phases due to AEs/SAEs, such as tether failure or implant re-operation, will no longer be followed at study-specific visits. These subjects have the option to consent and allow for continued monitoring by medical and radiographic record review through the end of the two-year Extended Follow-up Phase. Subjects who are withdrawn from the study also have the option to enroll in a separate LTFU observational study.

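### Section 8.5 closes extended-phase event recording at POD 730, but Visit 8 belongs to that phase and may fall as late as POD 820, so the two rules need reconciling

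*Combined protocol and SAP*

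**What the plan says.** Section 8.5 divides event recording by calendar day.

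- The period "Extended Follow-up Phase (POD 91-POD 730") takes every SAE whatever its cause. For non-serious events it is narrower: "Only AEs which are deemed “device related” will be recorded on study documents".
- The next period is "Long-term Follow-Up (POD 730 through approximately two years after skeletal maturity"). It is a chart review under a separate protocol, and the only class it names is "All SAEs identified from the medical records that are considered device related".
- The section then closes the list: "Only the AEs/SAEs indicated above will be recorded in a patient-specific study binder". It makes that binder the official record of events.

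The visit schedule uses a different end point. The Table of Study Procedures places Visit 8 under the Extended Follow-up Phase at 730 ± 90 days. Section 3.3.1 gives the visits in that phase a 90-day grace period, "making the initial study participation period 730 + 90 days after the day of surgery". The Visit 8 list in section 4.4.3 includes a spine film, its abstraction and "Complications review (research"), none of them limited to POD 730.

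**The concern.** A subject can attend a scheduled, in-window Visit 8 on POD 790 and be past the last day for which section 8.5 records non-serious device-related AEs. The class matters because of the definitions in section 6.6.2. A tether that has broken or lost tension is an SAE only if it is noted before maturity, the Cobb angle has worsened and re-operation is required. Without re-operation it is a non-serious device event, it is diagnosed on film, and Visit 8 supplies the last scheduled film.

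Section 6.1 makes the AE/SAE rate the primary endpoint, and section 6.3.2 reports device-related AE incidence with an exact 95% interval. Any event dropped under the literal rule makes the device look safer. Two abstractors applying different sections could also classify the same POD 790 finding differently.

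**Working it through.** **1. Day arithmetic.** Inputs: Visit 8 at 730 ± 90 (Table of Study Procedures) and the POD 730 cutoff (section 8.5).
- Earliest Visit 8: 730 − 90 = POD 640. Latest: 730 + 90 = POD 820, which reproduces the participation limit in section 3.3.1.
- Mismatch: 820 − 730 = 90 days (POD 731-820).
- The window holds 820 − 640 + 1 = 181 days, and 90/181 = 49.7% of them lie after the cutoff.

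**2. Which events the choice of rule affects on POD 731-820.**

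| Event | Extended-phase rule | Long-term rule |
|---|---|---|
| Device-related SAE | recorded | reported |
| SAE, not device related | recorded | not listed |
| Non-serious, device related | recorded | not listed |
| Non-serious, not device related | not recorded | not listed |

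The two middle rows depend on the rule. Section 4.7 does not fill them. It covers "serious, related adverse events after the subject completes or withdraws from the study", and a subject awaiting a late Visit 8 has done neither.

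**3. What share of findings first seen at Visit 8 falls after POD 730.** The documents give no visit dates or event rates, so these are assumptions: Visit 8 dates v spread evenly over POD 640-820, Visit 7 at POD 365, and onset uniform between the two films.
- Dated by detection: (820 − 730)/(820 − 640) = 90/180 = 50%.
- Dated by onset: (1/180) ∫ from 730 to 820 of (v − 730)/(v − 365) dv = [90 − 365 × ln(455/365)]/180 = (90 − 80.4)/180 = 5.3%.
- Range: if every Visit 8 is held by POD 730, both shares are 0%. If every one is on POD 820, they are 100% by detection and 90/455 = 19.8% by onset.

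**4. Effect on the reported incidence.** With 40 subjects, each affected subject moves the incidence by 1/40 = 2.5 percentage points. Illustration only, with exact (Clopper-Pearson) 95% intervals:
- 6/40 = 15.0% (5.7% to 29.8%)
- one dropped, 5/40 = 12.5% (4.2% to 26.8%)
- two dropped, 4/40 = 10.0% (2.8% to 23.7%)

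**5. Visit 5.** The window is 90 ± 21, so its latest day is 90 + 21 = POD 111, while recording of all AEs stops at POD 90. All SAEs and device-related AEs are still recorded after POD 90, so only non-serious events unrelated to the device drop out.

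**The case against.** The best defence is that POD 730 in section 8.5 is shorthand for the nominal two-year visit. Section 4.5 starts long-term follow-up after the extended phase, at approximately two years, and the Table counts the whole Visit 8 window as extended follow-up. Other provisions carry no day limit. Section 5.2 puts every AE and SAE on the complication form, section 8.1 monitors AEs throughout the study, and section 8.9 provides for asking subjects at follow-up about care sought between visits. The synopsis also makes implant failure on serial x-ray a safety endpoint of the extended phase, separately from AE recording.

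Much of this stands. A reader might infer from section 8.5 that failures seen at a late Visit 8 are lost altogether. The documents do not support that, because the film is still read and complications are still reviewed.

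The defence does not remove the conflict. The complication form of section 5.2 sits in the same binder that section 8.5 restricts, and section 8.5 already narrows section 5.2 from POD 91 by dropping non-device AEs. Collecting a finding at a visit does not settle whether it enters the AE record. Only section 8.5 addresses that, and its literal answer after POD 730 contradicts the schedule.

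It is also fair to object that the section asks for the onset date of an event, and that a late-seen finding may have begun before POD 730. Section 8.5 does not say whether onset or detection decides the recording period, so the size of the gap is open.

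**Conclusion.** The inconsistency is real and amounts to 90 days. Taken literally, section 8.5 leaves non-serious device-related AEs and non-device SAEs on POD 731-820 outside the official AE record of subjects still on study. This conflicts with the Table of Study Procedures and sections 3.3.1, 4.4.3 and 5.2.

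The number of events affected cannot be derived from the documents. A reader might infer that about half of Visit 8 findings go uncounted. That needs detection dating as well as evenly spread visits; with onset dating the same assumptions give about 5%. A reader might also infer that a two-year incidence is biased, but section 6.3.2 sets no two-year horizon for device-related AEs. Nor are the device-related stopping rules touched by the non-serious events, since section 6.6.2 concerns SAEs.

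The Visit 5 mismatch is minor. The main point is worth correcting because any error runs towards fewer device-related events and the remedy is small.

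**What to change.** In section 8.5:

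- End the extended recording period at the later of POD 730 and the completed Visit 8, and no later than POD 820. Ending it simply at Visit 8 would shorten recording for anyone seen before POD 730; a subject seen on POD 640 would lose 90 days.
- Start the long-term rule after that point.
- State that any device-related event first seen on the Visit 8 film counts in the device-related AE incidence of section 6.3.2 whatever the visit day. This settles the onset-or-detection question for those findings.
- If the Visit 5 boundary is changed too, use the later of POD 90 and the completed Visit 5, so that recording of all AEs never stops before POD 90.

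The cost is a short amendment with no added visits or films. Late attenders have up to 90 more days of event recording, and the reported rate may be slightly higher. Observation time will differ a little between subjects, so the report should give each subject's last recorded day.
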